2.2 Secondary Endpoints

The secondary endpoints will include the following additional safety endpoints which will be evaluated annually through Year 5 following treatment with the Alair System:

- Rates of Severe exacerbations (exacerbations / subject / year)
- Respiratory adverse events* (rates of respiratory adverse events, and proportion of subjects with respiratory adverse events)

Study Reference Number E7080

- Emergency room visits for respiratory symptoms (rates of emergency room visits and proportion of subjects with emergency room visits for respiratory symptoms)
- Hospitalizations for respiratory symptoms (hospitalizations/ subject/ year and the proportion of subjects with hospitalizations for respiratory symptoms)
- Respiratory Serious Adverse Events (detailed narratives will be provided for each event)
- Pre- and post-bronchodilator FEV₁

* A respiratory adverse event is defined as any sign, symptom, illness, clinically significant abnormal laboratory value, or other adverse medical event associated with the “Respiratory System” that appears or worsens in a subject during a clinical study, regardless of whether or not it is considered related to the procedure used as part of the protocol.

2.2.1 Hypotheses

There is no formal hypothesis for the secondary endpoints.

2.2.2 Statistical Methods

Descriptive statistics will be used to summarize the secondary endpoints. For continuous variables, summaries will include the sample size (N), mean, standard deviation, minimum, and maximum. Proportions will be presented with 95% confidence intervals.

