6.4 Secondary Analyses

Descriptive statistics will be performed for the following parameters for each 12-month period starting 6 weeks after the last treatment bronchoscopy and reported as including means and 95% CI:

- Rates of severe exacerbations (exacerbations / subject / year)
- Respiratory adverse events (rates of respiratory adverse events, and proportion of subjects with respiratory adverse events)
- Emergency room visits for respiratory symptoms (rates of emergency room visits, and proportion of subjects with emergency room visits for respiratory symptoms)
- Hospitalizations for respiratory symptoms (rates of hospitalizations, and proportion of subjects with hospitalizations for respiratory symptoms)
- Respiratory Serious Adverse Events (detailed narratives will be provided for each event)
- Pre- and post-bronchodilator FEV₁

Descriptive statistics for the subset of subjects enrolled at sites in the United States or in Canada alone will be provided for each of the secondary endpoints, although no conclusions can be drawn from either subset because of the smaller sample sizes.

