6.7 Data collection and Follow-up schedule

The planned study visits are outlined in the Study Flow Chart shown in Figure 2.

All data will be collected using appropriately designed case report forms (CRFs/eCRFs). Information on adverse events, incidences of OCS pulses for worsening of asthma symptoms, emergency room visits for respiratory symptoms, and hospitalizations for respiratory symptoms will be actively solicited by an appropriately qualified member of the clinical study site team during quarterly telephone contacts or at time of in-office visits.

Daily diaries will not be used in this clinical study, and all information solicited from the study subjects will be based on recall since the last contact (maximum recall time of 3 months). Episodes of worsening of asthma symptoms requiring treatment with oral corticosteroids, emergency room visits and hospitalizations for respiratory symptoms are rare events and are readily recalled for immediate past periods of 3 month duration. This approach will be consistent with data collection methodology in the AIR2 Trial.

The following data will be collected at the specified visits/evaluations:

Enrollment

- Medical history (including maintenance asthma medications and history of respiratory infections)
- Occurrence of events in the 12 month period prior to study enrollment
 - Severe exacerbations (pulses of systemic corticosteroids (tablets, suspension, or injection) for asthma symptoms)
 - Emergency room visits for asthma symptoms
 - Hospitalizations for asthma symptoms
- Forced Expiratory Volume in 1 second: FEV₁ (pre- and post-bronchodilator)
- Physical examination (including body weight)
- Chest X-ray (Lateral and PA)
- Asthma Quality of Life Questionnaire (AQLQ)

Treatment Period (Day of 1st bronchoscopy till 6 weeks after 3rd/last bronchoscopy)

- Adverse events
- Emergency room visits for respiratory symptoms
- Hospitalizations for respiratory symptoms
- FEV₁ (pre- and post-bronchodilator)

Phone Contact at every 3 Months between Annual Visits

- Adverse events
- Severe exacerbations
- Maintenance asthma medications
- Emergency room visits for respiratory symptoms
- Hospitalizations for respiratory symptoms

Annual Visits at 1, 2, 3, 4 and 5 years from end of Treatment Period (6 week visit following 3rd/last bronchoscopy)

- Adverse Events
- Severe exacerbations
- Physical examination (including body weight)
- Maintenance asthma medications

- Emergency room visits for respiratory symptoms

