4.4 Multivariable Analyses

Multivariate analyses will be conducted to explore the impact of baseline characteristics on treatment effect, for both the treatment period and the post-treatment period, including changes from year 1 to year 2 through year 5.

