4.5 Other Analyses

Demographic data including, but not limited to, age, race, gender and ethnicity, and baseline characteristics including, but not limited to, AQLQ (asthma quality of life questionnaire), maintenance asthma medication doses (see dose conversions in Section 6.5), pre- and post-bronchodilator forced expiratory volume in one second (FEV₁), prior 12 month history of severe exacerbations (use of systemic corticosteroids (tablets, suspension, or injection) for asthma

symptoms), and emergency room visits and hospitalizations for respiratory symptoms, will be reported for each subject. Procedural characteristics will also be summarized.

Demographic, baseline clinical information, and procedural characteristics will also be provided separately for the subsets of patients enrolled at sites in the United States and sites in Canada.

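### The SAP omits the 95% confidence intervals that the protocol requires for FEV1 and event rates, and neither document specifies FEV1 change from each subject's own baseline

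*SAP*

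**What the plan says.** Protocol 6.4 covers rates of severe exacerbations, respiratory adverse events, emergency visits and hospitalizations, and pre- and post-bronchodilator FEV1. These are to be described "for each 12-month period starting 6 weeks after the last treatment bronchoscopy and reported as including means and 95% CI".

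SAP 2.2.2 covers the same endpoints. It says "For continuous variables, summaries will include the sample size (N), mean, standard deviation, minimum, and maximum", and then "Proportions will be presented with 95% confidence intervals". It mentions no interval for a mean or a rate. SAP 2.2.1 adds that "There is no formal hypothesis for the secondary endpoints". The SAP revision history does not mention or explain the difference from the protocol.

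The data for a within-subject change are collected. Protocol 6.7 lists "Forced Expiratory Volume in 1 second", before and after bronchodilator, at enrollment and again at each annual visit. SAP 4.5 reports "pre- and post-bronchodilator forced expiratory volume in one second" as a baseline characteristic but does not link it to the follow-up values. The only analysis of change outside the primary endpoint is the exploratory modelling in SAP 4.4, "including changes from year 1 to year 2 through year 5". That starts at Year 1 and does not name FEV1.

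SAP 6.3 limits the missing-data sensitivity analysis to the primary endpoint.

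**The concern.** Longer-term safety is a stated objective of the study. Protocol 9.1 names bronchial stenosis, bronchiectasis and retained secretions as theoretical long-term risks, and Table 2 schedules chest X-ray only at screening. FEV1 is the one lung-function endpoint followed for five years, so its report should let a reader judge whether average lung function has held up.

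Yearly N, mean and SD do not do that well, for two reasons.

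- **Composition.** Baseline describes everyone, while Year 5 describes those with a Year 5 measurement. If the people lost differ in FEV1, the two means differ even when nobody has changed.
- **Precision.** The variance of a change depends on the within-subject correlation, and yearly summaries do not contain it. A reader can build a CI for each yearly mean from N, mean and SD, but not a valid one for the change.

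The SAP already uses paired data for the primary endpoint (2.1.3) but does not extend this to FEV1.

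**Working it through.** **What the plan gives.** Neither document contains an FEV1 SD, a within-subject correlation or a pattern of loss, so there is no FEV1 figure to reproduce. The one planning figure used here is attrition, from SAP 2.1.2: 200/(1 − 0.20) = 250, which agrees with the stated minimum enrollment. All other inputs below are assumptions, in points of FEV1 % predicted.

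**1. Who is in the yearly mean.** Spirometry is an office procedure; the quarterly telephone contacts do not include it (Protocol Table 2 and 7.3.12). SAP 2.1.3 accepts a subject for the primary endpoint who missed the annual visit but had a later contact, and that contact may be a phone call. Such a subject has no FEV1 for that year unless it is measured some other way. FEV1 loss can therefore exceed loss for the primary endpoint.

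**2. Shift from selective loss.** Let d be the fraction lost and g the mean of completers minus the mean of those lost. The whole-cohort mean is (1 − d) × completers + d × lost, so the completer mean exceeds it by d × g. With d = 0.20:

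| Assumed gap g | Shift d × g |
|---|---|
| 2.5 | 0.5 |
| 5 | 1.0 |
| 10 | 2.0 |
| 15 | 3.0 |

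If those lost have lower FEV1, the Year 5 mean is too high and a decline of that size is masked. If they have higher FEV1, the mean is too low and a decline is exaggerated. The table assumes that the gap persists in full to Year 5; with regression to the mean, only part of it carries over (step 4).

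**3. Precision of a Year 5 change.** With SD 15:

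- Means compared as independent: 15 × √(1/250 + 1/200) = 1.42.
- Paired, n = 200: 15 × √(2(1 − r))/√200 = 0.82, 0.67 and 0.47 for r = 0.7, 0.8 and 0.9.

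The 95% half-widths (1.96 × SE) over a range of assumed SDs are:

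| SD | Independent | Paired, r = 0.7 | Paired, r = 0.8 | Paired, r = 0.9 |
|---|---|---|---|---|
| 12 | 2.23 | 1.29 | 1.05 | 0.74 |
| 15 | 2.79 | 1.61 | 1.31 | 0.93 |
| 18 | 3.35 | 1.93 | 1.58 | 1.12 |

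**4. Whether a paired change in attendees is enough.** Take an assumed example: baseline mean 78, SD 15, r = 0.8, a true average decline of 2.0, and 21% loss that depends on low baseline FEV1, giving a baseline gap of 11.9. Completers start 0.21 × 11.9 = 2.5 points above the whole cohort. By Year 5, 0.8 × 2.5 = 2.0 of that remains.

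- Year 5 attendee mean minus full baseline mean: 2.0 − 2.0 = 0.0. The decline disappears.
- Paired change in attendees: −2.0 − (2.5 − 2.0) = −2.5. The decline is visible but overstated.
- True change: −2.0.

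A simulation of 4,000 cohorts of 250 gave the same three values. The paired change is the better summary here, but it is not free of bias, which is why attendees' and non-attendees' baselines should also be shown.

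**The case against.** The strongest reply is that these endpoints are descriptive, without a hypothesis, and that the protocol already requires the interval. SAP 2.2.2 says what summaries include and does not forbid more. That stands in part: the missing interval is a mismatch between SAP and protocol, so a reader who infers that no confidence interval is planned anywhere would be wrong. It does not answer the absence of a change from baseline in both documents.

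Second, attrition is partly examined. Protocol 6.3 compares five-year completers with those lost on baseline characteristics, and Protocol 6.2 counts FEV1 among the baseline clinical information. That comparison could reveal a baseline gap. However, it is made once, at five years, in support of the primary analysis, and the SAP does not carry it over. The supportive mITT set (SAP 3.1) limits changing membership between Year 1 and later years, but it does not restore comparability with baseline and is defined by primary-endpoint data, not FEV1.

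Third, nothing says that FEV1 will be summarised only in those measured; SAP 3.1 makes ITT primary. This is correct as to wording. With no imputation or model for FEV1, though, an available-case mean is the natural reading.

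Fourth, a reader might infer that FEV1 is the only objective measure of late airway harm, or that the output can neither show nor exclude a lasting loss. The documents support neither. Pulse oximetry is done at each annual visit, and respiratory hospitalizations and serious respiratory events with narratives are secondary endpoints. A large decline would show even in yearly means. Nor would a better mean detect rare stenosis: if 2 of 200 subjects each lost 30 points (an assumption), the mean would fall by 2 × 30/200 = 0.3, below even the smallest paired standard error of 0.47 at SD 15.

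**Conclusion.** The point holds as a reporting defect. The SAP omits intervals that the protocol requires for FEV1 and event rates, and neither document specifies within-subject FEV1 change although the data are collected. Yearly means of those measured can mask or exaggerate a modest average decline if loss is related to FEV1.

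The size cannot be derived from the documents. It is 0.5 to 3 points of % predicted in either direction under 20% loss and a persistent 2.5 to 15 point gap. The standard error of a Year 5 change is about 0.8 to 0.5 when paired, against 1.4 when means are treated as independent, under SD 15 and r from 0.7 to 0.9. Whether loss will be related to FEV1, and in which direction, is unknown.

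The defect does not touch the primary endpoint. Correcting it will not isolate a device effect either: in a single arm, ageing and disease progression are part of any change.

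**What to change.** In SAP 2.2.2:

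1. Restore the protocol's 95% CIs for continuous measures and for rates. Rate intervals should allow for repeated events within a subject, for example by a subject-level bootstrap or a negative binomial model.
2. Add change from own baseline in pre- and post-bronchodilator FEV1 at each annual visit, with 95% CI.
3. For each year, tabulate baseline FEV1 for subjects with and without a measurement.
4. As a supportive analysis, consider a repeated-measures model on all treated subjects. It is valid if data are missing at random, and does not cure loss driven by unobserved decline.

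The cost is SAP wording and some extra analysis work, with no new visits or data. The results stay descriptive and do not replace event reporting for rare structural harm.

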3 GENERAL STATISTICAL METHODS

3.1 Analysis Sets

The Intent-to-Treat (ITT) analysis set will consist of all subjects who have been administered at least one BT procedure. The modified Intent-to-Treat (mITT) analysis set will consist of all subjects who have been administered three BT procedures and have primary endpoint data at year 1 and year 2, 3, 4, or 5, as applicable. Analyses based on the ITT analysis set will be considered primary. Analyses based on the mITT analysis set will be considered supportive.

3.2 Control of Systematic Error/Bias

All subjects who have met the inclusion/exclusion criteria and have signed the ICF will be eligible for enrollment in the study. Visual and/or electronic data review will be performed to identify possible data discrepancies. Manual and/or automatic queries will be created in the EDC system and will be issued to the site for appropriate response. Site staff will be responsible for resolving all queries in the database.

3.3 Number of Subjects per Investigative Site

There is no minimum or maximum number of subjects to be enrolled at each center, however, centers in Canada will be limited to 20% of overall enrollment.

4 ADDITIONAL DATA ANALYSES

4.1 Interim Analyses

No formal interim analyses are planned for the PAS2 Study for the purpose of stopping the study early for declaring effectiveness or for futility.

4.2 Subgroup Analyses

Inferential analysis of the subset of subjects enrolled at sites in the United States or in Canada may lack the statistical power to demonstrate that the proportions are not substantially worse during each of the subsequent evaluation periods. Descriptive statistics for the point estimates introduced above will be presented for each subset, however, the primary endpoint analysis of the upper 95% confidence limit of the difference between the subsequent 12-month proportions (for Years 2, 3, 4, and 5) compared to the first 12-month proportion will not be required for the subsets.

Descriptive statistics for the subset of subjects enrolled at sites in the United States or in Canada alone will be provided for each of the secondary endpoints, although no conclusions can be drawn from either subset because of the smaller sample sizes.

Subgroup summaries may be performed for subgroups of interest (e.g. sex, age, etc.).

4.3 Justification of Pooling

The clinical study will be conducted under a common protocol for each investigational site with the intention of pooling the data for analysis. Every effort will be made to promote consistency in study execution at each investigational site.

Pooling analyses will be performed to assess the homogeneity of various characteristics and outcomes (e.g. primary endpoint, baseline characteristics, etc.) across investigational sites. If needed, virtual sites will be formed by combining low enrolling investigational sites within geographical region (United States and Canada); low enrolling sites are defined as having <5 subjects. The combining of investigational sites within region will be accomplished by taking the investigational site with the smallest enrollment and combining it with the investigational site with the largest enrollment (of those not enrolling at least 5 subjects).

Consistency will be investigated across country and investigational sites (after combining low enrolling sites), using statistical tests appropriate to the variable and an alpha level of 0.15.

4.4 Multivariable Analyses

Multivariate analyses will be conducted to explore the impact of baseline characteristics on treatment effect, for both the treatment period and the post-treatment period, including changes from year 1 to year 2 through year 5.

4.5 Other Analyses

Demographic data including, but not limited to, age, race, gender and ethnicity, and baseline characteristics including, but not limited to, AQLQ (asthma quality of life questionnaire), maintenance asthma medication doses (see dose conversions in Section 6.5), pre- and post-bronchodilator forced expiratory volume in one second (FEV₁), prior 12 month history of severe exacerbations (use of systemic corticosteroids (tablets, suspension, or injection) for asthma

symptoms), and emergency room visits and hospitalizations for respiratory symptoms, will be reported for each subject. Procedural characteristics will also be summarized.

Demographic, baseline clinical information, and procedural characteristics will also be provided separately for the subsets of patients enrolled at sites in the United States and sites in Canada.

4.6 Safety Analyses

Adverse events will be reported for the short-term (treatment period) and for the long-term (post-treatment period). The treatment period will be defined as the day of 1st procedure bronchoscopy till 6 weeks (41 days) after the last procedure bronchoscopy. The post-treatment period will begin at the end of the treatment period (i.e. beginning at 6 weeks [42 days] after the last procedure bronchoscopy) for patients who have at least one post-treatment visit (i.e. 6-week visit or later). Patients who do not have a post-treatment visit will not be counted in post-treatment summaries. Annual summaries will be based on a 365-day period beginning at 6 weeks (42 days) after the last procedure bronchoscopy.

Verbatim terms will be classified to preferred terms and system organ classes using the MedDRA dictionary. The preferred terms and system organ classes will then be tabulated by the treatment period and each year of follow-up. All reported adverse events will be summarized by the number of subjects reporting adverse events, system organ class (SOC), preferred term, severity, seriousness, duration, and relationship to procedure. In the summary of MedDRA coded terms, for the preferred terms listed in Table 3, the system organ class will be changed to “Respiratory, thoracic and mediastinal disorders”. The reason for the change in SOC is to conservatively report respiratory-related adverse events since the preferred terms in Table 3 represent events that could be related to respiratory function.

Table 3. Preferred Term that will have the system organ class (SOC) changed to “Respiratory, thoracic and mediastinal disorders” for summary tables

System Organ Class Code	System Organ Class	Preferred Term Code	Preferred Term
10005329	Blood and lymphatic system disorders	10020094	Hilar lymphadenopathy
10007541	Cardiac disorders	10007617	Cardio-respiratory arrest
10018065	General disorders and administration site conditions	10008469	Chest discomfort
		10008479	Chest pain
		10062501	Non-cardiac chest pain
10021881	Infections and infestations	10001076	Acute sinusitis
		10006451	Bronchitis
		10053160	Bronchitis viral
		10009137	Chronic sinusitis
		10022000	Influenza
		10023874	Laryngitis
		10067321	Laryngitis fungal
		10024968	Lower respiratory tract infection
		10025028	Lung abscess
		10028810	Nasopharyngitis

System Organ Class Code	System Organ Class	Preferred Term Code	Preferred Term
		10034835	Pharyngitis
		10034839	Pharyngitis streptococcal
		10035664	Pneumonia
		10035728	Pneumonia pneumococcal
		10035730	Pneumonia primary atypical
		10062352	Respiratory tract infection
		10060693	Respiratory tract infection bacterial
		10039083	Rhinitis
		10040753	Sinusitis
		10060841	Sinusitis bacterial
		10044008	Tonsillitis
		10046306	Upper respiratory tract infection
		10047473	Viral pharyngitis
		10051513	Viral sinusitis
		10047482	Viral upper respiratory tract infection
10022117	Injury, poisoning and procedural complications	10009913	Collapse of lung
		10069363	Traumatic lung injury
10028395	Musculoskeletal and connective tissue disorders	10050819	Musculoskeletal chest pain
10029104	Neoplasms benign, malignant and unspecified (incl cysts and polyps)	10062042	Lung neoplasm
10029205	Nervous system disorders	10034018	Parosmia
		10040744	Sinus headache

In addition to the complete tabulation of adverse events for all subjects enrolled in the study, adverse events will also be tabulated separately for the subsets of subjects enrolled in sites in the United States and the sites in Canada.

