6.5 Safety Analysis

Adverse events will be reported for the short-term (Treatment Period) and for the long-term (Post-Treatment Period). The Treatment Period will be defined at the Day of 1st procedure bronchoscopy till 6 weeks after the last procedure bronchoscopy. The Post-Treatment Period will begin at the end of the Treatment Period i.e. at beginning at 6 weeks after the last procedure bronchoscopy. Annual visits will be based on a 52 week period beginning at 6 weeks after the last procedure bronchoscopy.

An adverse event is defined as any sign, symptom, illness, clinically significant abnormal laboratory value, or other adverse medical event that appears or worsens in a subject during a clinical study, regardless of whether or not it is considered related to the procedure used as part of the protocol.

All adverse events reported during the study will be listed, documenting course, severity, possible relationship to procedure, and outcome. Verbatim terms will be classified to preferred terms and system organ classes using the MedDRA dictionary. The preferred terms and system organ classes will then be tabulated by the treatment period and each year of follow-up. All reported adverse events will be summarized by the number of subjects reporting adverse events, system organ class, preferred term, severity, duration, and relationship to procedure.

In addition to the complete tabulation of adverse events for all subjects enrolled in the study, adverse events will also be tabulated separately for the subsets of subjects enrolled in sites in the United States and the sites in Canada.

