7.3.9 Near-Term Follow-up

- Contact subject via telephone on Day 1, Day 2, and Day 7 after the treatment session to assess recovery.
- Remind subject to contact Investigator or a member of the clinical study staff at the Site if they experience any of the following:
 - Difficulty in breathing.
 - Night awakenings due to asthma symptoms.
 - Any changes in maintenance asthma medications.
 - Need to be seen by a physician prior to the next scheduled visit.
 - Any adverse events.

7.3.10 2-Week Follow-up (2 Weeks \pm 4 days after Treatment Session 1 and 2)

Examine the subject and perform the following evaluations:

- Focused physical exam including vital signs (heart rate, blood pressure, temperature, respiratory rate, SpO₂) and breath sounds.
- Review asthma symptoms, exacerbations, and asthma medication use.
- Solicit adverse events since last follow-up (See Section 8.0).
- Review Emergency Room visits for respiratory symptoms since last contact.
- Review hospitalizations for respiratory symptoms since last contact.
- Perform physical examination (including body weight).
- Pre-bronchodilator spirometry following a 12-hour abstinence from long-acting β_2 -agonist and a 4-hour abstinence from short-acting β_2 -agonists
- Post-bronchodilator spirometry 15 minutes after the administration of 4 puffs (total 400 μ g) of albuterol via spacer.
- If a subsequent treatment session is to be completed, see Section 7.3.6 and Section 7.3.7.

7.3.11 6-Week Follow-up (6 Weeks \pm 1 Week after last Bronchoscopy Session)

Examine the subject and perform the following evaluations:

- Focused physical exam including body weight, vital signs (heart rate, blood pressure, temperature, respiratory rate, SpO₂) and breath sounds.
- Review asthma symptoms, exacerbations, and asthma medication use.
- Solicit adverse events since last contact.
- Perform pre- and post-bronchodilator spirometry. Pre-bronchodilator spirometry following a 12-hour abstinence from long-acting β_2 -agonist and a 4-hour abstinence from short-acting β_2 -agonists.
- Review emergency room visits for respiratory symptoms since last contact.
- Review any hospitalizations for respiratory symptoms since last contact.

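### SAP 4.6 counts an adverse event on or after Day 42 in no period or annual table if the subject never has a visit at 6 weeks or later

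*SAP*

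**What the plan says.** SAP 4.6 splits adverse event reporting into two adjoining periods. The treatment period runs "till 6 weeks (41 days) after the last procedure bronchoscopy". The post-treatment period starts on the next day, "beginning at 6 weeks [42 days] after the last procedure bronchoscopy", but only "for patients who have at least one post-treatment visit (i.e. 6-week visit or later"). The SAP then states the consequence: "Patients who do not have a post-treatment visit will not be counted in post-treatment summaries". The yearly tables use the same starting point: "Annual summaries will be based on a 365-day period beginning at 6 weeks (42 days) after the last procedure bronchoscopy". Coded events are tabulated by treatment period and by year of follow-up.

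Protocol 6.5 defines the same two periods without any visit condition. It also says "All reported adverse events will be summarized by the number of subjects reporting adverse events", and SAP 4.6 repeats that sentence. The visit condition is therefore an addition made in the SAP.

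Protocol 7.3.11 allows the 6-week visit a tolerance of one week either side ("1 Week after last Bronchoscopy Session").

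Two other parts of the SAP treat a missed visit differently. In SAP 2.1.3, the Complete/Partial set for the primary endpoint takes in a subject who had a severe exacerbation in the period, however short the follow-up. SAP 6.4 step 6 plans a second summary of severe exacerbations, ER visits and hospitalizations that adds subjects with a severe exacerbation in the period to those with a visit.

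**The concern.** Entry to the post-treatment tables depends on attending a visit, and attendance can depend on the outcome being tabulated. A subject who has not yet been seen at 6 weeks, and who dies or has an SAE on or after Day 42 and never returns, can still be known to the sponsor. Protocol 8.0 requires SAE reports within 3 working days, and subjects are told to contact the site between visits. Such an event starts too late for the treatment period, and the subject is barred from the post-treatment period.

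Longer-term safety is a stated objective (Protocol 4.0) and a condition of the device's approval (Protocol 3.1). At stake is whether the period and annual AE/SAE tables contain every reported event and add up to the overall tabulation. The events most likely to be missing are those serious enough to end contact.

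The rule has a second weakness. Because the 6-week visit may precede Day 42, it can admit a subject who was never observed in the post-treatment period.

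**Working it through.** **1. Boundaries.** 6 x 7 = 42, so the SAP's Day 42 start is reproduced. Days 41 and 42 adjoin, so there is no calendar gap; any gap comes from the visit condition. The 6-week visit window is 42 - 7 to 42 + 7, that is Day 35 to Day 49.

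**2. Applying the SAP 4.6 rule to event onset.**

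| Onset (days after last bronchoscopy) | Has a 6-week or later visit | Has none |
|---|---|---|
| 35, 41 | treatment | treatment |
| 42, 43, 49, 60, 100 | post-treatment | neither |

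Year 1 starts on Day 42, so the right-hand cell of the second row is also absent from every annual table. A subject not yet seen can have such an event on Days 42 to 49 while still inside the visit window, and later if the 6-week visit is missed.

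**3. The converse case.** A subject seen on Day 36 and never again has had a 6-week visit, so enters the post-treatment denominator. Observed post-treatment time is zero.

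**4. Size per subject.** With x subjects with an event among n, omitting one of them changes the proportion from x/n to (x - 1)/(n - 1). For a single rare event (x = 1) the change is from 1/n to 0: 1/250 = 0.40 percentage points, or 1/300 = 0.33.

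**5. Direction.**
- Omitting a subject with an event: (x - 1)/(n - 1) is below x/n, so the proportion falls.
- Omitting a subject without an event: x/(n - 1) is above x/n, so it rises.
- Adding a subject with no observed time and no event: x/(n + 1) is below x/n, so it falls.

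The event count itself can only be too low. The net effect on proportions depends on the mix, which the documents do not give.

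**6. Expected number.** The documents give no event rate for subjects unseen at 6 weeks, so the annual rates here are assumptions. Over the 8 days from Day 42 to Day 49, expected events are N x rate x 8/365. At N = 250:
- 0.5% a year: 250 x 0.005 x 8/365 = 0.03
- 5% a year: 250 x 0.05 x 8/365 = 0.27
- 20% a year: 250 x 0.20 x 8/365 = 1.10

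These are upper bounds for that window, because they treat every subject as still unseen and never seen later. They exclude later events in subjects who miss the 6-week visit, whose number is not stated.

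**The case against.** The strongest case against is that this is a wording gap in descriptive tables with several backstops, and much of that stands.

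- **The event is not lost from the study.** A reader might infer that it vanishes. It does not: SAP 4.6 refers to a complete tabulation for all enrolled subjects, Protocol 6.5 lists every adverse event, respiratory SAEs have narratives (Protocol 5.6), and status reports must explain deaths (Protocol 15.0). None of these places the event in a period or year, which is what the tables are for.
- **Not every safety table is affected.** A reader might infer that all post-treatment safety output drops the subject. SAP 6.4 step 6 admits a subject with a severe exacerbation to the exacerbation, ER and hospitalization summaries. That contradicts 4.6 for those summaries and does nothing for a death or SAE without an exacerbation.
- **The affected group is narrow.** Any later visit over five years qualifies the subject, and so does a 6-week visit on Days 35 to 41. An SAE that merely delays the visit loses nothing. SAP 2.1.3 treats a phone call as a visit; SAP 4.6 does not say, and if it means the same the group is smaller still.
- **Planned attrition does not measure it.** One might take the under-5% yearly loss in Protocol 6.6 and compute 5% x 91/365 = 1.25%, or 3 to 4 of 250 to 300 subjects leaving before the first quarterly call. That call is three months after the 6-week evaluation (Protocol 7.3.12), so most such leavers would already have had the qualifying visit.
- **Absence is not always due to a serious outcome.** Ordinary loss to follow-up, or withdrawal for atypical anatomy (Protocol 7.3.7), also leaves no visit.

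**Conclusion.** The point holds for the period and annual AE/SAE tables. Read as written, SAP 4.6 counts a death or SAE with onset on or after Day 42 in no period and no year when the subject never has a visit at 6 weeks or later. This departs from Protocol 6.5, conflicts with the all-events sentence in SAP 4.6 itself, and is inconsistent with how SAP 2.1.3 and 6.4 step 6 treat severe exacerbations. The converse fault, admitting a subject seen only on Days 35 to 41, also follows from the text.

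The size is small: 0.33 to 0.40 percentage points for a single omitted event at N = 300 to 250, with the number of such subjects unknown. No hypothesis test depends on it. The documents do not support a claim that post-treatment rates or proportions are biased downward overall. They do support the narrower statement that event counts can only be understated. The change is still worth making because the exclusion can depend on the outcome and can remove the gravest events. The conclusion assumes that SAP 4.6 is programmed literally and that such an event is reported without a qualifying contact.

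**What to change.** Amend SAP 4.6 by the route in SAP 4.7:

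- Replace the exclusion sentence. Define the post-treatment set as all subjects with at least one BT procedure who have any contact (visit or call), reported event, hospitalization or death dated on or after Day 42 after the last procedure.
- Count exposure from Day 42 to the last such date. A visit on Days 35 to 41 alone then contributes neither a subject nor time.
- State that a phone call counts as a contact, and align SAP 4.6 with SAP 6.4 step 6 so that one subject is handled the same way in the AE, exacerbation, ER and hospitalization summaries of a period.

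Simply deleting the sentence, or counting everyone alive and not withdrawn at Day 42, would be worse: it would put subjects never observed after treatment into the denominators of proportions.

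The cost is a wording change and a little programming. SAP 2.1.3 already uses visit, call, event onset and hospitalization dates; only the date of death is added. Rates may become slightly less favourable. A subject without a contact would enter only by having an event, an asymmetry that SAP 2.1.3 and 6.4 already accept for severe exacerbations.
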